- Deaths will be summarized by three time periods (on-treatment vs. within 90 days of end of treatment vs. > 90 days after end of treatment) and cause of death. Deaths that occurred within 28 days after the last dose of study treatment are defined as on-treatment deaths. Death data will also be listed.
- Patients who withdraw from study treatment because of an AE will be listed separately for axitinib and MK-3475. Patient discontinuation will be determined from the end of treatment (EOT) evaluation (where reason for termination is “Adverse Event”) and the specific AE(s) will be determined from the AE CRF page (where action taken is “Withdrawn from Treatment”).
- SAEs and treatment-related SAEs will be summarized by MedDRA SOC and preferred term. Patients who experienced a SAE will be listed.

The following analyses will be performed for AEs of special interest (including, but not limited to, hepatic disorders [ALT, AST and bilirubin], thyroid dysfunction [hypo-/hyperthyroidism], diarrhea, colitis and pneumonitis).

- Hy's Law eDISH scatterplot of Maximum ALT vs. Maximum Total Bilirubin on treatment.

- Hy's Law eDISH scatterplot of Maximum AST vs. Maximum Total Bilirubin on treatment.
- The prevalence of AEs of special interest will be summarized by preferred term and maximum CTC severity grade.
- Descriptive statistics will be presented for time to AE onset (days), time to grade 2 and grade 3/4 AE onset.

For all safety analyses, only descriptive methods will be used without any formal statistical test.

Laboratory Tests

The number and percentage of patients who experienced laboratory test abnormalities will be summarized according to worst toxicity grade observed for each lab assay. The analyses will summarize laboratory tests on the entire treatment period, separately for the lead-in PK period and by cycle (Cycle 1, Cycle 2 and Cycles beyond 2), as well as for the entire treatment period starting at C1D1 (first dose of MK-3475) for patients receiving combination therapy.

For laboratory tests without CTC grade definitions, results will be categorized as normal, abnormal or not done.

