[figure not shown]
- **TWO EVENTS OF THE SAME CLUSTER WHERE ONE EVENT COMPLETELY CONTAINS THE OTHER EVENT**

- **CERTAIN PORTIONS OF TWO EVENTS IN THE SAME CLUSTER OVERLAP**

[figure not shown]

- **TWO EVENTS OF THE SAME CLUSTER ARE CONTIGUOUS TO EACH OTHER**

$$duration = enddate2 - startdate1 + 1$$

- **TWO EVENTS OF THE SAME CLUSTER ARE NON-OVERLAPPING**

$$duration = (enddate1 - startdate1 + 1) + (enddate2 - startdate2 + 1)$$

c. AE Prevalence

1. Definition

AE prevalence is defined as the number of patients with an AE in a particular time period (including both new cases with an onset date during the specified time period AND cases with an AE continued from a previous time period) divided by the number of patients at risk during the specified time period. The number of patients at risk includes all subjects except those who either have discontinued or died prior to the specified time period.

AE prevalence will be presented for the entire study period, separately for the lead-in PK period and by cycle (Cycle 1, Cycle 2 and Cycles beyond 2), as well as for the entire treatment period starting at C1D1.

2. Assumptions

For AE summaries of the study period starting at C1D1 the following apply:

- A patient is counted in the numerator if the patient has an onset date of the AE during Cycle 1 OR for patients with a 7 day lead-in PK period there is an increase in grade of the AE after the first dose of MK-3475 (C1D1) or if there is a decrease and then subsequent increase during treatment with the combination.
- The denominator will include subjects who have received at least one dose of MK-3475.

For AE summaries of the entire study period including by cycle (Lead-in PK period, Cycle 1, Cycle 2 and Cycles beyond 2) the following apply:

- Patients are counted for an AE in each cycle up until the cycle where the AE resolved. Thus, the calculation conservatively assumes that if the AE resolved in a cycle, it resolved at the end of the cycle.
- For Lead-in PK period, a patient is counted in the numerator if the patient has an onset date of the AE during the Lead-in period.
- For Cycle 1, a patient is counted in the numerator if the patient has an onset date of the AE during Cycle 1 OR an onset date during the Lead-in PK phase that is still ongoing in Cycle 1 (did not have a resolution date in the Lead-in phase).

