- For Cycle 2, a patient is counted in the numerator if the patient has an onset date of the AE during Cycle 2 OR an onset date during the Lead-in PK phase or Cycle 1 that is still ongoing in Cycle 2 (did not have a resolution date in the Lead-in phase or Cycle 1).

- For Cycles ≥ 2 , a patient is counted in the numerator if the patient has an onset date in Cycles ≥ 2 OR an onset date in a previous cycle that is still ongoing (did not have a resolution date in Cycle 1 or earlier).
- The denominator for a particular time period will include subjects who are at risk prior to the time period. The number at risk includes all subjects except those who either have discontinued (based on the 'Subject Summary' CRF) or died prior to the specified time period (i.e. Death Date based on 'Notice of Death' CRF is prior to start of time period).

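### SAP Appendix 1c: the by-cycle AE prevalence numerator can include patients who are no longer in its denominator

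*SAP*

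**What the plan says.** SAP Section 8.3.3.2 states the use: "The prevalence of AEs of special interest will be summarized by preferred term and maximum CTC severity grade".

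SAP Appendix 1, part c, first gives a definition. The numerator holds patients with the event in the period, both new cases and "cases with an AE continued from a previous time period"; this is "divided by the number of patients at risk during the specified time period". Patients who discontinued or died before the period are not at risk.

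The assumptions that follow turn this into programming rules for the lead-in, Cycle 1, Cycle 2 and later-cycle columns:

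- All cycles: "Patients are counted for an AE in each cycle up until the cycle where the AE resolved".
- Cycle 1 carries forward a lead-in event "that is still ongoing in Cycle 1 (did not have a resolution date in the Lead-in phase").
- Cycle 2 carries forward a lead-in or Cycle 1 event "that is still ongoing in Cycle 2 (did not have a resolution date in the Lead-in phase or Cycle 1").
- The last column counts an onset within it, "OR an onset date in a previous cycle that is still ongoing (did not have a resolution date in Cycle 1 or earlier").
- Denominator: "The denominator for a particular time period will include subjects who are at risk prior to the time period". Discontinuation is read from the Subject Summary CRF and death from the Notice of Death CRF.

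**The concern.** For a prevalence, every patient counted as a case must also be counted as at risk. The denominator rule removes early leavers. The carry-forward rules test one thing only, whether an earlier resolution date exists. A patient who leaves in the lead-in, Cycle 1 or Cycle 2 with an open event can therefore stay in later numerators after dropping out of the matching denominators.

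Open events in early leavers are foreseeable. Protocol Section 8.1.4.2 lets follow-up end when an event has stabilised rather than resolved. The events of special interest in SAP Section 8.3.3.2 (hepatic, thyroid, diarrhoea, colitis, pneumonitis) include ones that can lead to stopping a study drug under Protocol Table 6. The error runs in one direction, upward, and is largest for events that take patients out of the study. A reader of the later-cycle columns could conclude that toxicity persists among patients still under observation when some of those counted have left. Two programmers could also produce different tables from the same text.

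**Working it through.** The documents state no prevalence figure, so there is nothing to reproduce. The check has two parts.

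**1. Is the numerator limited to patients at risk anywhere?**

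- The general definition places the event in the period but does not say that the patient must be at risk then.
- The three carry-forward rules test only for a resolution date.
- The statement in part c that the method is conservative concerns when, within a cycle, an event that did resolve is taken to have ended. It does not cover events with no resolution date.
- Part b ends an unresolved event at death, but it governs duration of an event. Part c has no matching rule.
- No other place in the SAP or protocol supplies the restriction.

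**2. How large is the effect?**

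Inputs:

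- N, patients in the group: about 60 in total (SAP Section 8.1.3), up to 40 in the expansion cohort (SAP Section 4.2), or 3 as the target dose-finding cohort (Protocol Section 3.1.1.2).
- x, patients who left before the period with the event unresolved: not in the documents; assumed 1 to 6.
- m, at-risk patients with the event in the period: not in the documents; assumed 4, or as stated below.

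Formulas, if only these x patients have left:

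- Literal rule: (m + x)/(N − x)
- Numerator restricted to the denominator: m/(N − x)
- Difference: x/(N − x), whatever m is

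| N | m | x | Literal | Restricted | Difference (points) |
|---|---|---|---|---|---|
| 60 | 4 | 1 | 5/59 = 8.5% | 4/59 = 6.8% | 1.7 |
| 60 | 4 | 2 | 6/58 = 10.3% | 4/58 = 6.9% | 3.4 |
| 60 | 4 | 4 | 8/56 = 14.3% | 4/56 = 7.1% | 7.1 |
| 60 | 4 | 6 | 10/54 = 18.5% | 4/54 = 7.4% | 11.1 |
| 40 | 4 | 1 | 5/39 = 12.8% | 4/39 = 10.3% | 2.6 |
| 40 | 4 | 6 | 10/34 = 29.4% | 4/34 = 11.8% | 17.6 |

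If other patients leave without the event, the denominator shrinks further. With N = 60, four leavers, three of them with the event open, and m = 6, the literal rule gives 9/56 = 16.1% against 6/56 = 10.7%.

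Two limiting cases show that the literal ratio is not a proportion. With N = 60, m = 0 and x = 4 it gives 4/56 = 7.1% although no at-risk patient has the event. With N = 3, x = 2 and m = 1 it gives 3/1 = 300%. Small groups can arise because SAP Section 8.3.3 summarises secondary safety data by dose level and pools the two phases only at the MTD. One early leaver out of 3, with neither remaining patient affected, gives 1/2 = 50% instead of 0%.

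**The case against.** The best defence is that being ongoing in Cycle 2 presupposes that the patient has a Cycle 2. On that reading, the parenthesis only tells the programmer how to recognise an open event among patients who reached the cycle. Impossible values such as 300% suggest that the literal result was not intended. This reading is available, and it is probably what the authors meant. But the appendix is a programming specification and its only stated test is a missing resolution date, so a program that follows it carries these patients forward.

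Other limits stand:

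- A reader might infer that every fatal event stays prevalent in all later columns. The documents do not support that. Part b of the appendix allows for a resolution date equal to the date of death, and a fatal event closed that way is not carried forward. CRF practice is not stated.
- A reader might infer that everyone who stops for toxicity is miscounted. That depends on what the Subject Summary CRF records. Protocol Section 6.4 separates stopping treatment from leaving follow-up. If the form records study discontinuation, patients who only stop treatment remain in the denominator. Protocol Section 3.1 also lets a patient with toxicity from one drug continue the other.
- Later cycles form a single column, so only patients who leave before it begins can cause the mismatch.
- Large relative errors need particular counts. A threefold error (3/56 = 5.4% against 1/56 = 1.8%) requires two early leavers to share the same open preferred term when only one at-risk patient has it.
- The tables are descriptive, any error overstates toxicity, and the standard adverse event, SAE, discontinuation and death summaries do not use this rule.

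**Conclusion.** Wrong as written. The numerator and denominator rules in Appendix 1c use different patient sets, and the literal ratio departs from the appendix's own definition. The upward error is x/(N − x): 1.7 points for one affected patient among 60, 2.6 among 40, and much more in a dose-level group of a few patients. These sizes rest on assumed x.

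Fatal events are affected only if they are not closed at the death date. Patients who stop treatment are affected only if their Subject Summary status removes them from the denominator. The error is confined to the Cycle 1, Cycle 2 and later-cycle prevalence columns for events of special interest. The lead-in column carries nothing forward. The summary from Cycle 1 Day 1 is not affected, because its denominator is everyone given at least one dose of MK-3475. The DLT endpoint and MTD estimate do not use the rule. The documents do not support reading this as a flaw in the trial's main safety conclusions.

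**What to change.** Add one rule to Appendix 1c and apply it to the Cycle 1, Cycle 2 and later-cycle columns:

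*A patient is counted in a period's numerator only if the patient is in that period's at-risk denominator; an unresolved AE is not carried into periods starting after the patient's discontinuation or death.*

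Use the same Subject Summary and Notice of Death dates as the denominator, and state whether the Subject Summary status means discontinuation of treatment or of the study.

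The cost is a line or two in the programming specification. No new data are needed. The affected prevalences stay the same or fall; in the illustration with N = 60, m = 4 and x = 4, the value goes from 14.3% to 7.1%.

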Pharmacokinetic assessment: MK-3475 and axitinib do not have competing elimination/metabolism pathways, hence an overt PK interaction between the two drugs is not anticipated. However, pharmacokinetic assessments will be conducted in this study to confirm the absence of drug-drug interactions. To understand the PK effects of MK-3475 on axitinib, a 7-day lead-in period of single-agent axitinib will be included prior to Cycle 1 in all patients in the Dose Finding Phase and in at least 8 patients in the Dose Expansion Phase of the study. Axitinib has a plasma half life of 2.5-4.1 hours and is expected to reach steady-state within 2 to 3 days of dosing. MK-3475 has a long plasma half-life (21-28 days) and trough concentrations increase with successive doses until steady state, which is expected within 5 months of MK-3475 dosing. The administration of single agent MK-3475 to this patient population is not considered in this trial. Therefore, the effect of axitinib on MK-3475 will be evaluated by comparing MK-3475 pharmacokinetics at steady-state in the presence of axitinib with those reported for MK-3475 alone in prior studies. At least 8 patients (target is 8 PK evaluable patients) from the Dose Expansion Phase will participate in PK assessments, therefore these patients will undergo the 7-day lead-in period for axitinib. There will be no lead-in period for the remaining patients in the Dose Expansion Phase.

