MK-3475 and axitinib do not have competing elimination/metabolism pathways, hence an overt PK interaction between the two drugs is not anticipated. However, pharmacokinetic assessments will be conducted in this study to confirm the absence of drug-drug interactions. To understand the PK effects of MK-3475 on axitinib, a 7-day lead-in period with single-agent axitinib will be included prior to Cycle 1 in all patients in the Dose Finding Phase and in at least 8 patients in the Dose Expansion Phases of the study. On the contrary, the administration of single agent MK-3475 to this patient population is not considered in this trial. The effect of axitinib on MK-3475 will be evaluated by comparing MK-3475 trough concentrations at steady-state in the presence of axitinib with those reported for MK-3475 alone in prior studies. MK-3475 has a long half-life (21-28 days) and an increase in trough concentration over time is expected.

Archived tumor biospecimens, and baseline de novo biospecimens from metastatic lesions will be collected for all patients in the dose expansion cohort. Every effort will be made to obtain a second biopsy at the time of first tumor assessment at 12 weeks. Biomarker studies on tumor and blood biospecimens will be carried out to help understand the mechanism of action of the axitinib plus MK-3475 combination, as well as potential mechanisms of resistance. Such results may help in the future development of this combination. Analyses using translational approaches may also result in the identification of potential biomarkers of response to the axitinib plus MK-3475 combination, ultimately leading to the development of a patient selection strategy for further clinical investigation. As such, collection of tumor and blood biospecimens at baseline and on study will be of paramount importance.

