8.3.3. Analysis of Safety Endpoints

Analysis Set

- Summaries and analyses of the primary safety endpoint will be based on the per protocol analysis set. Summaries and analyses of all other safety parameters will include all patients in the Safety Analysis Set.

- Secondary safety endpoint data will be summarized by dose level (pooling patients treated at the MTD from both phases of the study).
- Adverse events and laboratory tests will be summarized for the following study periods: entire study period and by cycle (Cycle 1, Cycle 2 and Cycles beyond 2) in the Safety Analysis Set; the PK lead-in period for those patients receiving at least one dose of axitinib during the 7 day PK lead-in period; and the treatment period starting at C1D1 for patients receiving the combination treatment.

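### SAP Appendix 1c and SAP Section 8.3.3 give different denominators for lead-in AE prevalence; programmed literally, the appendix would dilute it about 2.1-fold at the planned sizes

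*SAP*

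**What the plan says.** SAP Appendix 1, part c, specifies AE prevalence. Its definition announces the columns: "AE prevalence will be presented for the entire study period, separately for the lead-in PK period and by cycle", and also for the treatment period from Cycle 1 Day 1 (C1D1).

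The assumptions then fall into two groups.

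- For the period from C1D1 the denominator is tied to exposure: "The denominator will include subjects who have received at least one dose of MK-3475".
- The second group opens with "For AE summaries of the entire study period including by cycle (Lead-in PK period, Cycle 1, Cycle 2 and Cycles beyond 2", so the lead-in is handled together with the cycles. The lead-in numerator is onset of the AE during the lead-in ("For Lead-in PK period, a patient is counted in the numerator" on that condition). The group closes with a common denominator: "The number at risk includes all subjects except those who either have discontinued" or died before the period. No exposure condition is attached to the lead-in.

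SAP Section 8.3.3 sets the populations for AE and laboratory summaries. It assigns the entire-period and by-cycle summaries to the Safety Analysis Set. It lists the lead-in separately, as "the PK lead-in period for those patients receiving at least one dose of axitinib during the 7 day PK lead-in period".

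On who has a lead-in, SAP Section 2.1 places it before Cycle 1 "in all patients in the Dose Finding Phase and in at least 8 patients in the Dose Expansion Phases of the study". Protocol Section 3.1 adds: "There will be no lead-in period for the remaining patients in the Dose Expansion Phase".

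**The concern.** A patient who goes straight to Cycle 1 has no lead-in in which an AE can start. Counting that patient in the lead-in denominator lowers the percentage without adding any information. Appendix 1 is the programming specification, so its wording is what a programmer is likely to code. It also groups the lead-in with the summaries that Section 8.3.3 runs on the Safety Analysis Set, which makes a denominator of all treated patients an easy choice.

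At stake is the prevalence summary for AEs of special interest in SAP Section 8.3.3.2, which covers hepatic disorders, thyroid dysfunction, diarrhoea, colitis and pneumonitis among others. With a diluted lead-in column beside a Cycle 1 column in which every counted patient was exposed, the two columns would not be comparable. Part of any rise between them would come from the denominator.

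**Working it through.** **Inputs**

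- Dose Finding patients, D: about 20 DLT-evaluable (SAP Section 8.1.3). Dose finding ends once at least 10 are evaluable at the highest dose with a DLT rate below 0.33 (SAP Section 8.1.1), so D = 10 serves as a low case. D = 12 is four cohorts of the target size of 3.
- Expansion patients: up to 40 (Protocol Summary, Sample Size Determination).
- Expansion patients with a lead-in, E: at least 8 (SAP Section 2.1; Protocol Section 3.1). Values above 8 are assumptions.
- Planned total: about 60 (SAP Section 8.1.3).

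**The plan's own figure.** 20 + 40 = 60, which reproduces the planned total. The documents state no lead-in denominator and no prevalence figure.

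**Step 1: does the appendix rule exclude anyone from the lead-in?** It removes only patients who discontinued or died before the period. The lead-in comes first, so this removes essentially nobody, and the denominator is all treated patients, D + 40.

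**Step 2: the denominator under Section 8.3.3.** Patients dosed with axitinib in the lead-in: D + E. At the planned sizes this is 20 + 8 = 28. The other 60 − 28 = 32 patients (53.3%) have no lead-in.

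**Step 3: dilution factor.** The numerator is the same under both rules, so the factor is (D + 40) / (D + E). The printed prevalence is the true prevalence divided by this factor.

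| D | E | All treated | With lead-in | Factor | A true 30% prints as |
|---|---|---|---|---|---|
| 20 | 8 | 60 | 28 | 2.14 | 14.0% |
| 20 | 10 | 60 | 30 | 2.00 | 15.0% |
| 20 | 12 | 60 | 32 | 1.88 | 16.0% |
| 20 | 16 | 60 | 36 | 1.67 | 18.0% |
| 20 | 20 | 60 | 40 | 1.50 | 20.0% |
| 12 | 8 | 52 | 20 | 2.60 | 11.5% |
| 10 | 8 | 50 | 18 | 2.78 | 10.8% |

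In counts: if 7 patients had a given AE in the lead-in (an assumed number), the two rules give 7/28 = 25.0% and 7/60 = 11.7% at the planned sizes.

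The ends of the table are scenarios, not limits. If all 40 Expansion patients had a lead-in, the factor would be 60/60 = 1.00.

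**The case against.** The strongest reply is that Section 8.3.3 has already fixed the population. If the appendix only describes how to compute prevalence within that population, its reference to all subjects means all lead-in patients, and nothing is diluted. The appendix also speaks of patients at risk, and someone with no lead-in is arguably never at risk in it.

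The first part has weight. A reader might infer that the SAP is bound to print an understated lead-in prevalence; the documents do not support that, because one section gives the correct population. The second part does not rescue the appendix, which defines being at risk by two exclusions only, discontinuation and death. It states an exposure condition for the C1D1 period and none for the lead-in.

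Three other inferences go further than the documents:

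- *That the lead-in is the only axitinib-alone safety data.* Patients who stop MK-3475 may continue on axitinib alone (Protocol Section 5.2.4.2), with AEs still recorded (Protocol Appendix 6).
- *That the lead-in is the planned safety reference for what MK-3475 adds.* Its stated purpose is pharmacokinetic, and no AE comparison of lead-in with Cycle 1 is planned. Such a comparison would be limited even with correct denominators: 7 days stand against 21, and Cycle 1 prevalence carries forward lead-in events that are still ongoing.
- *That the appendix also misdefines discontinuation for the later columns.* It relies on the Subject Summary CRF, whose content is not shown, so no error can be established.

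**Conclusion.** The point stands as an inconsistency within the SAP. Appendix 1c and Section 8.3.3 give different denominators for the lead-in column, and the appendix rule, followed as written, yields a wrong figure.

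The size is conditional. At the planned sizes the lead-in prevalence would be diluted 2.14-fold; the range is roughly 1.5 to 2.8 over the scenarios shown. This rests on the literal reading of the appendix, on the planned 40 Expansion patients, on the assumed D and E, and on ignoring early discontinuations. It would be too strong to say that more than half of the patients necessarily lack a lead-in: with 20 Dose Finding patients that fails once 10 or more Expansion patients have one.

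The consequence is confined to descriptive prevalence of AEs of special interest. The DLT endpoint, the MTD and the efficacy analyses do not use this denominator.

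**What to change.** Add one sentence to SAP Appendix 1, part c, under the assumptions for the entire study period including by cycle: *For the lead-in PK period, the denominator is the patients who took one or more doses of axitinib in that period, as in Section 8.3.3.* The rule for Cycle 1 and later columns can stay as it is.

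The cost is one sentence and one programming filter on lead-in dosing. No new data are needed.
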